4.3 Justification for Dose

Combination of regorafenib and nivolumab was evaluated in a Phase 1b trial of Japanese patients with advanced pMMR/MSS CRC and gastric cancer and demonstrated clinically relevant activity greater than that expected from either agent alone with confirmed ORR of 33% and median PFS of 7.9 months in CRC and 44% for gastric cancer and median PFS 5.6 months (Fukuoka et al. 2020). The combination was well tolerated at regorafenib starting dose of 80 mg once daily for 21 days on and 7 days off and nivolumab 3 mg/kg Q2W

In the dose escalation part of the study, regorafenib doses of 80, 120 or 160 mg were administered once daily for 21 days on and 7 days off with intravenous nivolumab 3 mg/kg Q2W. Three dose limiting toxicities (DLTs) were observed during dose-escalation with

Page 35 of 135

regorafenib 160 mg, including Grade 3 maculopapular rash, colonic perforation and proteinuria. There was no DLT observed with 80 mg or 120 mg dose of regorafenib. Maximum tolerated dose for the combination based on pre-defined DLT criteria was deemed to be 120 mg. In the first 18 patients treated at 120 mg dose of regorafenib in the dose expansion cohort, all but one required dose reduction to 80 mg for AEs mostly related to frequent Grade 3 skin toxicities. All remaining 18 patients were treated with regorafenib starting dose of 80 mg and tolerated treatment well. Grade \geq 3 treatment related adverse events occurred in 20 patients (6 at 80 mg, 11 at 120 mg and 3 at 160mg). The common Grade \geq 3 events (>10%) were rash (12%), palmar-plantar erythrodysesthesia (10%), and proteinuria (12%). None of the patients treated at 80 mg dose had Grade \geq 3 rash or palmar-plantar erythrodysesthesia, while 5 events (20%) each were reported at 120 mg dose. Grade \geq 3 treatment related adverse each for hypertension, proteinuria and hepatic dysfunction.

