Regorafenib will be given orally every day for 3 weeks of each cycle. Each treatment cycle will be 28 d in duration. Regorafenib will be given as 30 mg tablets QD for 3 weeks of every 4 weeks (i.e., 3 weeks on, 1 week off) as a starting dose of 90 mg. If starting dose of 90 mg daily is well tolerated (absence of any grade rash/HFSR or other Grade 2 or higher clinically significant toxicity; lab abnormalities of any grade that resolve to \leq Grade 1 within 72 hours are acceptable) dose can be escalated to 120 mg orally daily anytime after Cycle 1 starting with C2D1. Sponsor should be informed immediately, if the Investigator decides to not escalate the dose to 120 mg despite meeting the criteria.

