Table 6–2 outlines different regorafenib dose levels for the purpose of dose modification. In case a dose reduction for regorafenib is necessary, the study intervention will be administered as outlined in Table 6–2 to Table 6–6.

	days on, 7 days off)	Daily Regorafenib (21 days on, 7 days off from cycle 2 onwards if escalation if feasible)
Dose Level 0	90 mg	120 mg
Dose Level -1	60 mg	90 mg
Dose Level -2	NA	60 mg ^a

Table 6–2 Dose Levels for Regorafenib

Abbreviations: NA = Not applicable

a) If reductions are required resulting in regorafenib daily dose of less than 60 mg, then regorafenib will be permanently discontinued.

Table 6–3	Dose Modification/Dose Interruption Guide for Regorafenib-Related
Toxicities	

CTCAE Grade	Occurrences	Dose Interruption	Dose modification (when resuming treatment)
Grade 0-2 ^c	Any	No change	No change
Ore de Of	1 st and 2 nd occurrence	Hold until recovery to <g2 baselinea</g2>	Restart at same dose level or reduce 1 dose level (at the investigator's discretion)
Grade 3 ^c	3 rd occurrence	Hold until recovery to <g2 baselinea</g2>	Reduce 1 dose level or consider permanent discontinuation ^b
Grade 4 ^c	Any	-	Discontinue

Abbreviations: CTCAE = Common terminology criteria for adverse events; G = Grade; HFSR = Hand-foot skin reaction

a) Excludes alopecia, non-refractory nausea/vomiting, lymphopenia and asymptomatic laboratory abnormalities. Treatment can be resumed with Grade 2 fatigue or hypothyroidism.

- b) If reductions are required resulting in regorafenib daily dose of less than 60 mg, then regorafenib will be permanently discontinued. If toxicity returns to Grade 0-1 after dose reduction, dose reescalation is permitted in the subsequent cycle at the investigator's discretion. Participants requiring a delay of >4 weeks should discontinue regorafenib treatment. However, continuation of regorafenib may be considered if, in the investigator's opinion, the participant may continue to benefit from the regorafenib treatment, and after consultation with Sponsor.
- c) Discontinuation is required for severe bleeding necessitating urgent medical intervention, gastrointestinal perforation or fistula of any grade and posterior reversible encephalopathy syndrome (PRES) of any grade.

Page 54 of 135

Skin toxicity grade (CTCAE)	Occurrence	Dose Interruption	Dose modification (when resuming treatment)	

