Grade 1	Any	Maintain dose level and institute supportive measures immediately for symptomatic relief	No Change	
	1 st occurrence	Interrupt therapy for a minimum of 7 days, until toxicity resolves to Grade 0–1	Institute supportive measures and continue same dose or consider decrease by 1 dose level	
Grade 2	No improvement within 7 d or 2 nd occurrence	Interrupt until toxicity resolves or improves to G1.	When resuming treatment, treat at reduced dose level or consider discontinuation ^a	
	3 rd occurrence	Discontinue		
	1 st occurrence	Institute supportive measures immediately. Interrupt therapy for ≥ 7 d until toxicity resolves or improves to G1.	When resuming treatment, decrease by 1 dose level	
Grade 3	2 nd occurrence	Institute supportive measures immediately. Interrupt therapy for ≥ 7 d until toxicity resolves or improves to G1.	When resuming treatment, decrease by 1 additional dose level or consider discontinuation ^a	
	3 rd occurrence	Discontinue		

Table 6–4Regorafenib Dose Modification/Dose Interruption Guidance: HFSR/Palmar-Plantar Erythrodysesthesia Syndrome

Abbreviations: CTCAE = Common terminology criteria for adverse events; G = Grade; HFSR = Hand-foot skin reaction

a) If reductions are required resulting in regorafenib daily dose of less than 60 mg, then regorafenib will be permanently discontinued. If toxicity returns to Grade 0-1 after dose reduction, dose reescalation is permitted in the subsequent cycle at the Investigator's discretion. Participants requiring a delay of >4 weeks should discontinue regorafenib treatment. However, continuation of regorafenib may be considered if, in the investigator's opinion, the participant may continue to benefit from the regorafenib treatment, and after consultation with Sponsor.

Page 55 of 135

Table 6–5	Regorafenib Dose Modification Guidance: Non-Immune Toxicities:
Hypertensic	n

CTCAE Grade	Suggested regorafenib dose interruption	Suggested regorafenib dose modification
Specific guidance for	or HYPERTENSION	
Grade 1	No change.	Consider increased BP monitoring
Grade 2	If symptomatic, hold until symptoms resolve and diastolic BP ≤ 90 mmHg. Treat with anti-hypertensive medications	At restart, continue at the same dose level
	Hold until diastolic BP ≤ 90 mm Hg, and if symptomatic, until symptoms resolve. Treat with additional anti-hypertensive medications	At restart, continue at the same dose level.
Grade 3	If BP is not controlled with the addition of new or more intensive therapy.	Reduce by 1 dose level

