	If G3 hypertension recurs despite dose reduction and optimal antihypertensive therapy	Reduce another dose level or consider discontinuation ^a
Grade 4 ^b	Discontinue	

Abbreviations: BP = Blood pressure; CTCAE = Common terminology criteria for adverse events; G = Grade; Hg = Mercury

a) If reductions are required resulting in regorafenib daily dose of less than 60 mg, then regorafenib will be permanently discontinued. If toxicity returns to Grade 0-1 after dose reduction, dose reescalation is permitted in the subsequent cycle at the investigator's discretion. Regorafenib cannot be interrupted for more than 28 consecutive days including the drug holidays. However, continuation of regorafenib may be considered if, in the investigator's opinion, the participant may continue to benefit from the regorafenib treatment, and after consultation with Sponsor.

b) This includes hypertensive crisis per CTCAE v 5.

Table 6–6	Dose Modification/Dose Interruption Guide for Regorafenib-related
Toxicities: L	iver Function Test Increases Related to Regorafenib ^a

Increases in AST/ALT/Bilirubin	Occurrence	Dose Interruption	Dose Modification (when resuming treatment)
(from baseline within normal limits) AST and/or ALT < 3 times ULN or total bilirubin < 1.5 times ULN	Any	Continue dosing	No Change
(from baseline AST/ALT more than 1 and up to 3 times ULN) AST or ALT more than 3 and up to 5 times the ULN	Any	Continue dosing	No Change
(from baseline within normal limits) AST or ALT more than 3 and up to 5 times the ULN or total bilirubin more	1 st occurrence	Delay dosing until return to Grade ≤ 1 or baseline	Reduce 1 dose level ^b
than 1.5 and up to 3 times the ULN	Re-occurrence	Discontinue	
(from baseline any grade) AST or ALT more than 5 times the ULN or total bilirubin more than 3 times the ULN	1 st occurrence	Delay dosing until return to Grade ≤ 1 or baseline	If the potential to reinitiate regorafenib is considered to outweigh the risk of hepatotoxicity: reduce 1 dose level
	Re-occurrence	Discontinue	
(from baseline any grade) AST and/or ALT > 20 x ULN	Any	Discontinue	

Page 56 of 135

Increases in AST/ALT/Bilirubin	Occurrence	Dose Interruption	Dose Modification (when resuming treatment)
AST and/or ALT > 3 x ULN with concurrent bilirubin > 2 x ULN	Any	Discontinue°	

Abbreviations: ALT=Alanine aminotransferase; AST=Aspartate aminotransferase; ULN = Upper limit of normal

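### For Grade 2 HFSR, symptomatic Grade 2 hypertension and some liver-test rises, Table 6-3 and the event-specific regorafenib tables cannot both be followed, and no passage says which table governs

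*Protocol*

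**What the plan says.** Protocol Section 6.6.1 introduces the regorafenib tables with one linking sentence: "In case a dose reduction for regorafenib is necessary, the study intervention will be administered as outlined in" Tables 6-2 to 6-6. It names them together and gives no order of precedence.

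- **Table 6-3** covers regorafenib-related toxicities by CTCAE grade. Grade 0-2 events, at any occurrence, lead to no interruption and no dose change. For a first or second Grade 3 event the drug is held until recovery, and the choice on resuming is "Restart at same dose level or reduce 1 dose level", left to the investigator. A third Grade 3 event leads to a reduction or to considering permanent discontinuation. Grade 4 leads to discontinuation. Footnote a, attached to the Grade 3 hold cells, excludes asymptomatic laboratory abnormalities among other things. Footnote c lists events that always require discontinuation.
- **Table 6-4** is titled for HFSR/palmar-plantar erythrodysesthesia (PPE), but its grade column is headed "Skin toxicity grade (CTCAE". A first Grade 2 event reads "Interrupt therapy for a minimum of 7 days". A first Grade 3 event reads "When resuming treatment, decrease by 1 dose level".
- **Table 6-5** covers hypertension. Symptomatic Grade 2 hypertension is held until symptoms resolve and diastolic pressure meets a limit.
- **Table 6-6** covers liver-test rises in multiples of ULN. For a first rise above 3 and up to 5 × ULN from a normal baseline it says "Delay dosing until return to Grade ≤ 1 or baseline", then reduce one level. A re-occurrence means discontinuation.

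Section 7.1 makes withdrawal of regorafenib for unacceptable toxicity depend on the guidance in Section 6.6 as a whole.

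**The concern.** One event can fall under two tables that tell the site to do different things, and the choice of table decides whether a participant continues, pauses, is reduced or stops regorafenib for good. Skin events matter for this combination. Section 4.3 reports of the earlier trial: "In the first 18 patients treated at 120 mg dose of regorafenib in the dose expansion cohort, all but one required dose reduction", mostly because of skin toxicity, and the present protocol allows escalation to 120 mg.

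Participant safety is at stake first. The reporting is affected too. Protocol Section 9.4.5 summarizes AEs leading to discontinuation or modification, and SAP v3.0 Sections 5.4.1.2 and 5.6.1 repeat the AE and dose-modification analyses for the final report. If sites resolve the conflict differently, those tables partly reflect how each site read the protocol. AE severity itself is graded by CTCAE and not by these tables, so any effect on it is indirect.

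**Working it through.** No statistical figure is involved, so the check sets the instructions side by side.

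**1. HFSR, Table 6-3 against Table 6-4.** Grade 1 is compatible. The other six cells are:

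| Grade, occurrence | Table 6-3 | Table 6-4 | Can both be followed? |
|---|---|---|---|
| 2, 1st | no change | interrupt at least 7 days; same dose or consider one level lower | No |
| 2, 2nd (or no improvement in 7 days) | no change | interrupt; reduced level or consider discontinuation | No |
| 2, 3rd | no change | discontinue | No |
| 3, 1st | hold; same dose or one level lower | interrupt at least 7 days; one level lower | Yes, by reducing |
| 3, 2nd | hold; same dose or one level lower | interrupt at least 7 days; one further level lower or consider discontinuation | Yes, by reducing |
| 3, 3rd | hold; one level lower or consider permanent discontinuation | discontinue | Yes, by discontinuing |

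Three of the six cells are incompatible. In the other three, Table 6-3 allows something that Table 6-4 does not.

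The Grade 3 difference still has consequences. Take a participant at 90 mg who is never escalated or re-escalated. Table 6-2 has one step down, to 60 mg, and a need to go below 60 mg means permanent discontinuation. Under Table 6-4 the first Grade 3 event gives 90 − 30 = 60 mg. A second reduction would give 60 − 30 = 30 mg, which is below 60 mg, so regorafenib stops. Under Table 6-3 the same participant may restart at 90 mg after both events.

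**2. Hypertension, Table 6-3 against Table 6-5.** Symptomatic Grade 2: no change against a hold. Both cannot be followed.

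**3. Liver tests, Table 6-3 against Table 6-6.** Table 6-3 uses CTCAE grades and Table 6-6 uses ULN multiples. The documents do not print the mapping, so each possibility was checked for AST/ALT above 3 and up to 5 × ULN from a normal baseline:

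- If Grade 2: no change, against delay and reduce, then discontinue on re-occurrence. Incompatible.
- If Grade 3: compatible at the first event by reducing. At the second, restart against discontinue. Footnote a may remove this for asymptomatic rises.
- If Grade 4: discontinue, against delay and restart one level lower. Incompatible.

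Some difference remains under every mapping. Grade 2 is an assumption. The restart target in Table 6-6 (Grade 1 or lower, or baseline) fits with the rise being above Grade 1.

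**4. Inside Table 6-6.**

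- Row 1 (normal baseline, continue dosing) joins its limits, AST/ALT below 3 × ULN and bilirubin below 1.5 × ULN, with the word *or*. AST 8 × ULN with normal bilirubin meets row 1 through the bilirubin limit. It also meets the row for more than 5 × ULN, which says delay.
- The row for more than 5 × ULN has no upper limit. AST 25 × ULN meets it (delay, possible restart) and also the row for more than 20 × ULN (discontinue).

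**5. Search for a precedence rule.** Section 6.6 has a rule to take the more conservative approach, but it applies when a toxicity cannot be attributed to one of the two drugs. It does not rank the regorafenib tables. Sections 6.6.1, 6.6.2 and 7.1 contain no such rule either.

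**The case against.** The strongest reply is that the layout already shows general and specific guidance. Table 6-6 repeats the Table 6-3 title and adds liver tests, Table 6-5 labels itself as specific to hypertension, and Table 6-4 would have no purpose if Table 6-3 governed HFSR. HFSR in the Table 6-3 abbreviation line does not prove that the table covers it. Section 6.6.1 is also headed as recommendations, and Section 6.6 asks investigators for a careful decision. This reply has weight: most readers would probably use the specific table. But the protocol does not say so, Section 7.1 relies on Section 6.6 as a whole, and the inference does nothing for the overlapping rows inside Table 6-6. The *or* in row 1 can be called a literal reading, since a later row plainly addresses rises above 5 × ULN. The missing upper limit on that later row cannot be explained in the same way.

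A reader might also infer four stronger points that the documents do not support:

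- *That the tables conflict over rash.* No row of Table 6-4 or 6-6 names rash, and Sections 2.3 and 4.3 report rash and PPE as separate events. Only the column heading of Table 6-4, and the escalation criterion in Section 6 ("absence of any grade rash/HFSR"), leave its place open.
- *That Table 6-3 has no exceptions.* Footnote a is a partial one. It sits at the Grade 3 hold cells, so it does not reach the Grade 0-2 row, and it does not mention HFSR or hypertension.
- *That all six HFSR cells contradict each other.* Only the three Grade 2 cells do.
- *That the Grade 3 or higher rates in Sections 2.3 and 4.3 size the problem.* The HFSR conflict lies mainly at Grade 2. The 20% AST rate comes from regorafenib with pembrolizumab in hepatocellular carcinoma. The rash and PPE rates pool doses up to 160 mg, with none of these events at Grade 3 or higher at 80 mg.

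Finally, SAP v3.0 describes the analysis once all participants have discontinued, so an amendment may come too late to affect dosing. That changes the remedy, not the finding.

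**Conclusion.** The point holds in a limited form. Table 6-3 has no exclusion for HFSR, hypertension or Grade 0-2 liver-test events, and nothing states that Tables 6-4 to 6-6 override it. The instructions are incompatible for Grade 2 HFSR at all three occurrences, for symptomatic Grade 2 hypertension, and for some liver-test rises. The liver example with no change rests on the assumed CTCAE Grade 2 mapping. For Grade 3 HFSR the two tables can be reconciled by following Table 6-4, but Table 6-3 permits a same-dose restart that Table 6-4 does not. Table 6-6 contains at least two overlaps of its own. Rash is unresolved rather than contradictory.

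The number of participants affected cannot be derived, because the documents print no Grade 2 rates for these events. Sample size and error rates are not touched. The matter should be corrected because it concerns continuing or stopping a study drug and the correction is cheap. No view is taken on which instruction is right.

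**What to change.** The passages must be reconciled, with the sponsor deciding the clinical content:

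- In Section 6.6.1 and in the title of Table 6-3, state which toxicities Table 6-3 does not cover and which table governs each of them.
- Align the title and grade-column heading of Table 6-4 so that rash falls in one table only.
- Make the rows of Table 6-6 mutually exclusive, including the joining word in row 1 and the upper limit of the row for more than 5 × ULN.

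While participants are on treatment, this costs wording in an amendment and a clarification letter to sites, with no new data, visits or participants. If treatment has already ended, disclose the ambiguity in the clinical study report next to the summaries of dose modifications and discontinuations.

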6.6.2.1 Criteria to Resume Nivolumab Treatment

Participants who require delay of nivolumab should be re-evaluated weekly or more frequently if clinically indicated and resume nivolumab dosing when re-treatment criteria are met at D1 of a next planned cycle.

Participants may resume treatment with nivolumab when the drug-related AE(s) resolve to Grade ≤ 1 or baseline value (please refer to Appendix 9: Guidance for Management of Immune-Related Adverse Events), with the following exceptions:

Participants may resume treatment in the presence of Grade 2 fatigue

Participants with persistent Grade 1 pneumonitis after completion of a steroid taper over at least 1 month may be eligible for retreatment if discussed with and approved by Sponsor.

Participants with drug-related endocrinopathies adequately controlled with only physiologic hormone replacement may resume treatment after consultation with the Sponsor.

6.6.2.2 Management of Immune-Mediated AEs

Immune-mediated adverse events (IMAEs) are AEs consistent with an immune-mediated mechanism or immune-mediated component for which non-inflammatory etiologies (e.g., infection or tumor progression) have been ruled out. IMAEs can include events with an alternate etiology which were exacerbated by the induction of autoimmunity. Information supporting the assessment will be collected on the participant's case report form.

Because of the potential for clinically meaningful nivolumab related AEs requiring early recognition and prompt intervention, management algorithms have been developed for suspected pulmonary toxicity, GI toxicity, hepatotoxicity, endocrinopathy, skin toxicity, neurological toxicity, cardiac toxicity and renal toxicity. These adverse event management algorithms are included in Section 10.9.

These general guidelines constitute guidance to the Investigator and may be supplemented by discussions with the Sponsor. A general principle is that differential diagnoses should be diligently evaluated according to standard medical practice. Non-inflammatory etiologies should be considered and appropriately treated. Corticosteroids are a primary therapy for immune related adverse events. The oral equivalent of the recommended IV doses may be considered for ambulatory patients with low-grade toxicity. The lower bioavailability of oral corticosteroids should be taken into account when switching to the equivalent dose of oral corticosteroids. Consultation with a medical or surgical specialist, especially prior to an invasive diagnostic or therapeutic procedure, is recommended.

6.6.2.3 Treatment of Nivolumab Related Infusion Reactions

Since nivolumab contains only human immunoglobulin protein sequences, it is unlikely to be immunogenic and induce infusion or hypersensitivity reactions. However, if such a reaction were to occur, it might manifest with fever, chills, rigors, headache, rash, pruritus, arthralgias,

27 JAN 2021

hypotension, hypertension, bronchospasm, or other allergic-like reactions. All Grade 3 or 4 infusion reactions should be reported within 24 hours to the Sponsor and reported as an SAE if it meets the criteria. Infusion reactions should be graded according to NCI CTCAE, v5.0 guidelines. Treatment recommendations are provided below and may be modified based on local treatment standards and guidelines, as appropriate:

For Grade 1 symptoms:

• Remain at bedside and monitor participant until recovery from symptoms. The following prophylactic premedications are recommended for future infusions: diphenhydramine 50 mg (or equivalent) and/or acetaminophen/paracetamol 325 to 1000 mg at least 30 minutes before additional nivolumab administrations.

For Grade 2 symptoms:

- Stop the study drug infusion, begin an IV infusion of normal saline, and treat the participant with diphenhydramine 50 mg IV (or equivalent) and/or acetaminophen/paracetamol 325 to 1000 mg; remain at bedside and monitor participant until resolution of symptoms. Corticosteroid and/or bronchodilator therapy may also be administered as appropriate. If the infusion is interrupted, then restart the infusion at 50% of the original infusion rate when symptoms resolve; if no further complications ensue after 30 minutes, the rate may be increased to 100% of the original infusion rate. Monitor participant closely. If symptoms recur, then no further study medication will be administered at that visit.
- For future infusions, the following prophylactic premedications are recommended: Diphenhydramine 50 mg (or equivalent) and/or acetaminophen/paracetamol 325 to 1000 mg should be administered at least 30 minutes before nivolumab infusions. If necessary, corticosteroids (up to 25 mg of hydrocortisone or equivalent) may be used.

For Grade 3 or 4 symptoms:

• Immediately discontinue infusion of study drug. Begin an IV infusion of normal saline and treat the participant as follows: Recommend bronchodilators, epinephrine 0.2 to 1 mg of a 1:1000 solution for subcutaneous administration or 0.1 to 0.25 mg of a 1:10,000 solution injected slowly for IV administration, and/or diphenhydramine 50 mg IV with methylprednisolone 100 mg IV (or equivalent), as needed. Participant should be monitored until the Investigator is comfortable that the symptoms will not recur. Study drug will be permanently discontinued. Investigators should follow their institutional guidelines for the treatment of anaphylaxis. Remain at bedside and monitor participant until recovery of the symptoms.

In case of late-occurring hypersensitivity symptoms (e.g., appearance of a localized or generalized pruritus within 1 week after treatment), symptomatic treatment may be given (e.g., oral antihistamine or corticosteroids).

Additional details on the immune mediated AEs of nivolumab, including results from other clinical studies, are also available in the nivolumab IB.

